3.3 Subject enrolment and randomization

Investigator(s) should keep a record of subjects considered for, and included in the study. This pre-screening/screening log will be evaluated periodically by AstraZeneca or its delegates during routine monitoring visits.

The investigator or designee will:

1. Obtain signed informed consent, and assent when applicable, from the potential subject before any study specific procedures are performed.
2. Assign each potential subject a unique enrollment number, beginning with 'E1001001 via interactive web/voice response system (IWRS/IVRS).
3. Determine subject's eligibility. See sections 3.1 and 3.2

- During the screening period, subjects will be screened with medical history, physical examination, spirometry and routine laboratory tests. These assessments may be carried out over two test days in order to minimize tests while entry criteria are being established

If subjects continue to meet entry criteria their allergic status will be documented by skin testing against a panel of common airborne allergens.

Note: If subjects meet entry criteria to progress to the screening allergen challenge triad then the visits for the screening allergen challenge must be conducted over three consecutive days.

- An allergen challenge will be performed to confirm the presence of an early and late phase response. Only subjects with a documented early ($\geq 20\%$ fall in FEV_1) and late ($\geq 15\%$ fall in FEV_1) asthmatic response to inhaled incremental allergen challenge will be eligible for randomisation. The screening allergen challenge can be repeated at the discretion of the Investigator, as per [REDACTED] SOPs.
4. Assign eligible subject unique randomization code via IWRS/IVRS. Randomisation codes will be assigned strictly sequentially per site, ie, lowest available randomisation number will be assigned.

If a subject withdraws from participation in the study, then his/her enrolment/randomisation code cannot be reused.

3.4 Procedures for handling incorrectly enrolled or randomized subjects

Subjects who fail to meet the eligibility criteria should not, under any circumstances, be enrolled or receive study medication. There can be no exceptions to this rule. Subjects who

are enrolled, but subsequently found not to meet all the eligibility criteria must not be randomized or initiated on treatment, and must be withdrawn from the study.

Where a subject does not meet all the eligibility criteria but is randomized in error, or incorrectly started on treatment, the Investigator should inform the AstraZeneca study physician immediately, and the subject should be discontinued from the study

3.5 Methods for assigning treatment groups

Subjects will be randomized in a 1:1 ratio to benralizumab or placebo.

In order to have balanced number of subjects for the outcomes from induced sputum, blood, bone marrow and bronchoscopy measures, randomization will be stratified by the following types of measurements: 1) bone marrow plus bronchoscopy measurements, 2) bronchoscopy measures only, and 3) neither bone marrow nor bronchoscopy measurements.

Randomization codes will be assigned strictly sequentially as subjects become eligible for randomization.

Specific information concerning the use of the IWRS/IVRS will be provided in the separate manual.

Subjects who fail to meet the inclusion/exclusion criteria should not, under any circumstances, be randomized or receive study medication. There can be no exceptions to this rule.

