1.4 Study Design

This randomized, double-blind, parallel group, placebo-controlled study will evaluate the effect of a fixed 30 mg dose of benralizumab administered SC every 4 weeks for 3 doses on allergen-induced inflammation in subjects with mild atopic asthma challenged with an inhaled allergen.

Approximately 38 non-smoking men and women (18 – 65 years of age) corticosteroid-free (oral and inhaled) mild, atopic asthmatics who have demonstrated a dual (early and late) asthmatic response to inhaled allergen challenge at screening will be recruited to complete the study.

This study will include 6 centres in [REDACTED] Canada. All centres will participate in the characterization of the early and late asthmatic response and induced sputum collections. A subset of 5 centres will conduct the endobronchial biopsy collections, and bone marrow aspirates will be conducted at one centre only.

After enrolment and confirmation of entry criteria, subjects will enter a 4 week run-in period during which their suitability for randomization will be confirmed and to allow resolution of airway inflammation induced from the allergen challenge screening assessments. Subjects

who meet all the eligibility criteria will return to the clinic for collection of tissue samples according to the participation of the study site (sputum, bone marrow aspirates, lung biopsies and blood) for assessment of baseline inflammation. This will be conducted at 2 visits over a 3 day period.

[figure not shown]
Subjects will then be randomized to receive either benralizumab 30 mg SC or matching placebo (1:1). Subjects will receive 2 additional doses of study treatment every 4 weeks for a total of 3 doses.

Twenty eight days following the first dose, subjects will return to the clinic for assessment of dosing effects on airway hyperresponsiveness (MCh PC20) and collection of a blood sample for eosinophil and serum biomarkers measurements and a sputum sample for eosinophil and biomarker measurements.

Twenty eight days following the second dose, subjects will return to the clinic for assessment of dosing effects on baseline inflammation in the lung biopsies (only sites participating in the bronchial biopsy collections) and collection of a blood sample (all sites) for blood eosinophil measurements. Subjects will then receive a third dose of study treatment and return to the clinic no less than 7 days later for the first allergen challenge period.

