4.1 Enrolment/screening period (Visit 1 – Visit 3)

Each potential subject must provide written informed consent prior to any study specific procedures and undergo assessments applicable for the visit (see [Table 1](#)).

Subjects must sign the Informed Consent Form (ICF) prior Visit 1 procedures.

A sub-set of up to 22 subjects recruited at one of the study centres will be required to provide consent to supply a sample of their bone marrow. Subjects recruited at 5 of the 6 study centres will be required to provide consent for endobronchial biopsies. These consents are included in the main subject informed consent form.

At Visit 1a the following assessments will be conducted:

- Collection of demographics and evaluation of the health and asthma status of the subject including height and weight, physical examination, vital signs, ECG, clinical chemistry and hematology, urinalysis, spirometry, medical and asthma history, pregnancy test

Other study assessments and procedures to be performed at enrolment Visit 1 are mentioned in [Table 1](#). It is preferred that Visit 1a is conducted over two days, however, Visit 1a may be conducted over a period of up to two weeks to allow any repeat assessments that may need to be made.

Subjects who do not meet the Visit 1a assessment criteria must not be enrolled in the study.

Subjects who meet eligibility criteria from V1a will return for the allergen challenge screening assessments at Visit 1b, Visit 2 and Visit 3. Visit 1b, Visit 2 and Visit 3 must be conducted over 3 consecutive days.

At Visit 1b the following assessments will be conducted:

- Spirometry
- Methacholine PC20 test to determine that a subject has hyper-responsive airways for inclusion criteria and to calculate the concentration of allergen to be used on each subject for the inhaled allergen challenge test at Visit 2 ([Cockcroft et al 1987](#)). The calculated MCh PC20 at the site will be recorded in the CRF.
- Induced sputum procedure to determine ability of subject to provide a viable sputum sample and to determine the pre-allergen challenge eosinophil count.

Note that the skin prick test to confirm atopy and identify the specific allergen and allergen sensitivity for inhalation challenge testing may be conducted at Visit 1a or Visit 1b at the preference of the study site investigator.

At Visit 2 assessment the following assessments will be conducted:

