8.5.1 Analysis of the primary variable (s)

8.5.1.1 Allergen induced change in percentage of eosinophils in induced sputum 7-hr post allergen challenge during Allergen Challenge 1

The null hypothesis is that the allergen induced change in percentage of eosinophils in induced sputum 7-hr post allergen challenge during Allergen Challenge 1 in the Benralizumab group is equal to the allergen induced change in percentage of eosinophils in induced sputum 7-hr post allergen challenge during Allergen Challenge 1 in the Placebo group. The alternative hypothesis is that the allergen induced change in percentage of eosinophils in induced sputum 7-hr post allergen challenge during Allergen Challenge 1 in the Benralizumab group is not equal to that in Placebo group, ie,:

*H*₀: Allergen Induced Change_{7-hr post challenge at Allergen Challenge 1 (Benralizumab)} = Allergen Induced Change_{7-hr post challenge at Allergen Challenge 1 (Placebo)}

*H*_a: Allergen Induced Change_{7-hr post challenge at Allergen Challenge 1 (Benralizumab)} \neq Allergen Induced Change_{7-hr post challenge at Allergen Challenge 1 (Placebo)}

The primary analysis method for the allergen induced change on Visit 11 (7-hr post challenge) and 12 (24-hr post challenge) will be compared between Benralizumab and Placebo using a repeated measures analysis. The dependent variable will be the allergen induced change in percentage of eosinophils in induced sputum at 7-hr and 24-hr post allergen. Treatment group will be fitted as an explanatory variable pre-dose allergen induced change at Screening will be fitted as a covariate. Visit will be fitted as a categorical variable, and the variance-covariance matrix will be assumed to be unstructured. If the procedure does not converge the compound symmetric variance-covariance matrix will be used instead. The least squares mean for the difference in treatment groups using the interaction between visit and treatment group its 95% CI, and the 2-sided p-values will be reported for each visit.

8.5.1.2 Maximum percent decrease in FEV₁ in late asthmatic response (LAR_{3-7 hr}) on Visit 11 during Allergen Challenge 1

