The null hypothesis is that the maximum percent decrease in FEV₁ in late asthmatic response (LAR_{3-7 hr}) on Visit 11 in Benralizumab group is equal to the maximum percent decrease in FEV₁ in late asthmatic response (LAR_{3-7 hr}) on Visit 11 in Placebo group. The alternative hypothesis is that the maximum percent decrease in FEV₁ in late asthmatic response (LAR_{3-7 hr}) on Visit 11 in Benralizumab group is not equal to that in Placebo group, ie,:

H₀: Maximum percent decrease in FEV₁ in LAR_{3-7 hr} visit 11 (Benralizumab) = Maximum percent decrease in FEV₁ in LAR_{3-7 hr} Visit 11 (Placebo)

H_a: Maximum percent decrease in FEV₁ in LAR_{3-7 hr} visit 11 (Benralizumab) ≠ Maximum percent decrease in FEV₁ in LAR_{3-7 hr} Visit 11 (Placebo)

Maximum percent decrease in FEV₁ at LAR_{3-7 hr} on Visit 11 will be compared between Benralizumab and Placebo using an ANCOVA. The dependent variable will be maximum percent decrease in FEV₁ at LAR_{3-7 hr}. Treatment group will be fitted as an explanatory variable and the corresponding pre-dose FEV₁ value at Screening will be fitted as a covariate. The least squares mean for the difference in treatment groups and its 95% CI, and the 2-sided p-values will be provided.

As a supportive analysis to the primary analyses the time adjusted AUC of FEV₁ at LAR_{3-7 hr} will be analyzed and summarized descriptively as for maximum percent decrease in FEV₁.

The above analyses will be repeated at allergen challenge 2 triad.

FEV₁ at both pre- and post-challenge timepoints and minimum FEV₁ post-challenge for LAR_{3-7 hr} will also be summarized descriptively by visit (Visit 2, 11 and 14).

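### Randomisation is stratified by measurement type but the efficacy models omit the stratum, so the tests may be conservative; Sections 3.3 and 3.5 also describe code assignment differently

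*Protocol*

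**What the plan says.** Section 3.5 sets the allocation: "Subjects will be randomized in a 1:1 ratio to benralizumab or placebo". It adds that "randomization will be stratified by the following types of measurements". The three levels are marrow sampling together with bronchoscopy, bronchoscopy alone, and neither procedure. The synopsis repeats this. The stated purpose is to balance numbers across the sputum, blood, marrow and bronchoscopy outcomes.

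Section 1.4 ties the strata to centres: "A subset of 5 centres will conduct the endobronchial biopsy collections, and bone marrow aspirates will be conducted at one centre only". Section 4.1 agrees: "Subjects recruited at 5 of the 6 study centres will be required to provide consent for endobronchial biopsies". It also limits marrow sampling to a subset of at most 22 subjects at its one centre.

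Section 8.5.1 writes out both primary models term by term:

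- **Sputum eosinophils (repeated measures):** treatment, the allergen-induced change at screening, visit, and the visit-by-treatment interaction. "Visit will be fitted as a categorical variable, and the variance-covariance matrix will be assumed to be unstructured".
- **Late asthmatic response (LAR), ANCOVA:** "Treatment group will be fitted as an explanatory variable and the corresponding pre-dose FEV₁ value at Screening will be fitted as a covariate".

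The models in Section 8.5.2 follow the same pattern. None of them names stratum or centre.

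On code assignment, Section 3.3 says: "Randomisation codes will be assigned strictly sequentially per site". Section 3.5 describes sequential assignment as subjects become eligible and does not mention site.

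**The concern.** Stratified randomisation forces the arms to be balanced on the stratum, so the treatment contrast is nearly free of between-stratum variation. A model without the stratum still counts that variation as residual noise. The standard error is then overstated, the interval is too wide, and the true two-sided error rate is below 5%.

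Strata could plausibly differ. Stratum 1 comes from one centre and stratum 3 is in effect the single centre without biopsies. Challenge, spirometry and sputum induction are done at the sites. Procedures before the primary challenge at Visit 11 also differ: strata 1 and 2 have bronchoscopy at Visit 8, and stratum 1 has a marrow aspirate at Visit 10. What is at stake is precision in a trial of about 38 subjects.

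The second issue is that a list run per site and a list run per measurement type are different procedures, and the protocol does not say how they combine.

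**Working it through.** **1. The plan's sample size (Section 8.2).** Two-sided 5%, 80% power, normal approximation: n per arm = 2 × (1.960 + 0.842)² × (SD/difference)², where 2 × (1.960 + 0.842)² ≈ 15.70.

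- LAR: 15.70 × (12/11)² = 18.7, so 19 per arm. Power at 19 is 80.7% (78.5% from the noncentral t).
- Sputum: difference 0.8 × 20.8 = 16.64; 15.70 × (17.3/16.64)² = 17.0, so 17 per arm. Power at 19 is 84.2% (82.2% from the t).

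The stated 19 per arm is reproduced and is driven by LAR. It does not depend on the stratum.

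**2. Effect of omitting the stratum.** Let rho be the share of residual variance, after the screening covariate, that lies between strata. The protocol gives no value. With balance within strata:

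- ratio of interval widths, without to with stratum = 1/√(1 − rho)
- true two-sided alpha without stratum = 2 × [1 − Φ(1.96/√(1 − rho))]

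For example, at rho = 0.10 the ratio is 1/√0.90 = 1.054, and alpha is 2 × [1 − Φ(2.066)] = 3.9%.

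The formulas were checked by simulating a single-timepoint ANCOVA with 38 subjects, SD 12, difference 11, blocks of 4, and a covariate unrelated to outcome. Block size and stratum sizes are assumptions. Results for strata of 22/10/6:

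| rho | Excess width, formula | Simulated mean width, without / with | Alpha without, formula | Simulated alpha, without / with | Simulated power, without / with |
|---|---|---|---|---|---|
| 0 | 0% | 15.9 / 16.0 | 5.0% | 5.4% / 5.4% | 78% / 78% |
| 0.05 | 2.6% | 15.9 / 15.6 | 4.4% | 4.5% / 4.7% | 78% / 79% |
| 0.10 | 5.4% | 16.0 / 15.2 | 3.9% | 4.2% / 5.1% | 78% / 81% |
| 0.20 | 11.8% | 16.0 / 14.3 | 2.8% | 3.3% / 5.0% | 79% / 85% |

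The simulated excess, which includes the cost of two degrees of freedom, is 15.924/15.605 = 2.0%, 15.975/15.222 = 4.9% and 16.014/14.312 = 11.9%. Strata of 14/18/6 give the same pattern. At rho = 0, adding the stratum widens the interval by 16.009/15.897 = 0.7%.

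**3. If the screening covariate already carries the stratum difference.** Assume outcome and covariate both have total variance 1, share the same stratum effects (share R of the variance), and correlate 0.5 within strata. The pooled slope is R + 0.5(1 − R). Residual variance is 1 − slope² without stratum and 0.75(1 − R) with it.

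- R = 0.10: slope 0.55; 0.6975 against 0.675; width ratio √1.033 = 1.017.
- R = 0.20: slope 0.60; 0.640 against 0.600; width ratio √1.067 = 1.033.

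Dividing by the 1.007 cost from step 2 leaves about 1.0% and 2.6%.

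**4. Section 3.3 against Section 3.5.** Stratum 1 sits in one centre and stratum 3 in effect in another, so a blocked list per site would roughly balance both. If every subject at the marrow centre gave marrow and blocks were of 4, the arms would differ by 0 among 20 subjects and by at most 2 among 22. Stratum 2 is spread over the remaining biopsy centres, plus any subjects at the marrow centre who do not give marrow. Separate lists by stratum within site would satisfy both sections, but the protocol does not say that this is meant.

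**The case against.** The strongest case against the point is that the planned analysis is valid and keeps its design power. Unadjusted simulated power is 78 to 79% in every row of the table, in line with the t-based 78.5% for LAR. A reader might infer that the trial loses power on both primary endpoints. The figures do not support that: adjustment would add power above the design level if strata differ, and the plan forgoes that gain. The calculation also uses the LAR effect in a single-timepoint model; the two-visit sputum model was not simulated.

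Residual differences may also be small. All subjects must be dual responders, challenges follow common procedures, and sputum differentials are read at one central laboratory. The sputum model adjusts for the same quantity at screening, which brings it towards the 1 to 3% case. The argument is less secure for LAR, whose covariate is worded as a screening FEV₁ value. Stratum 2 pools several centres, so a stratum term would not remove all centre variation.

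The strata are justified by balance of numbers and are not presented as prognostic. Section 8.1 leaves full details to the SAP, which could add the term. That is fair, but the protocol does spell out both primary models without it.

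A reader might also infer from Section 3.3 that the marrow stratum would be unbalanced. That is not shown: marrow comes from one centre, and a blocked list there would roughly balance it.

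**Conclusion.** The point holds as a modest improvement in precision together with a wording inconsistency. The models omit a factor by which the trial randomises. To the extent that strata differ after the screening covariate, intervals are too wide and the test is conservative. The estimate is not biased, false positives are not increased, and the sample size is not wrong for this reason.

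The size is unknown: nil without stratum differences, about 2%, 5% and 12% of interval width at 5%, 10% and 20% residual stratum variance, and about 1 to 3% if the covariate carries the difference. These figures rest on assumed stratum sizes, blocks of 4 and, for the last case, a within-stratum correlation of 0.5. The marrow endpoints are unaffected, since all their subjects lie in one stratum. The conflict between Sections 3.3 and 3.5 needs clarifying; nothing stronger follows from the text.

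**What to change.** - Add randomisation stratum (three levels) as a fixed effect to the sputum repeated-measures model, to the LAR and early-response ANCOVAs, and to the secondary models that use all subjects.
- Use two levels in models confined to the biopsy subset, including the repeats at Allergen Challenge 2, which only that subset undergoes. Use no stratum term for the marrow subset.
- Reconcile Section 3.3 with Section 3.5, for example by stating that codes are assigned sequentially within randomisation stratum, or within stratum and site if that is how the system works.

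The cost is protocol and SAP wording before unblinding and at most two residual degrees of freedom, which widens intervals by under 1% if strata turn out not to differ.

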3.6 Methods for ensuring blinding

The study will be conducted in double-blind fashion. AstraZeneca staff involved in the study, the subjects, and the investigators involved in the treatment of the subjects or in their clinical evaluation will not be aware of the treatment allocation.

Placebo solution will be visually matched with benralizumab solution. Both benralizumab and placebo will be provided in an accessorized pre-filled syringe (APFS).

Maintaining the blind to the subject's blood, sputum and bone marrow eosinophil and basophil counts

While not entirely specific, subjects on active benralizumab treatment are expected to have lower eosinophil and basophil counts than subjects on placebo. Procedures to mitigate unblinding on this basis include:

- From Visit 4 on, eosinophil, basophil and monocyte counts will be redacted from the full hematology and leukocyte PD markers reports
- From Visit 4 on, eosinophil and basophil assessments conducted in induced sputum, endobronchial biopsies, blood and bone marrow at McMaster University Laboratory will be conducted by separate

laboratory staff who do not have communication with the subjects and are not involved in any other data collection in the study (i.e. adverse event reporting, clinical testing procedures conducted at the study site, laboratory procedures conducted at the study site). To further maintain blinding of personnel at the McMaster clinical site the following procedure will be followed by the McMaster central laboratory staff:

- Samples at the time of collection by study site staff will be labelled with subject identification, study, test and date.
- An individual not involved with the study will prepare an additional layer of blinding so that each sample cannot be traced back to the subject identification number. This will require a separate coded number.
- The results will be collected and maintained on a password protected computer that is regularly backed up. Results will not be shared with others who collect data.
- Once all procedures have been completed for a subject, the separate code can be broken and subject data entered into the database

3.7 Methods for unblinding

Individual treatment codes, indicating the treatment randomisation for each randomised subject, will be available to the Investigator(s) or pharmacists from the IVRS/IWRS. Routines for this will be described in the IVRS/IWRS user manual that will be provided to each centre.

The treatment code should not be broken except in medical emergencies when the appropriate management of the subject requires knowledge of the treatment randomisation. The Investigator documents and reports the action to AstraZeneca, without revealing the treatment given to subject to the AstraZeneca staff.

AstraZeneca retains the right to break the code for SAEs that are unexpected and are suspected to be causally related to an investigational product and that potentially require expedited reporting to regulatory authorities. Treatment codes will not be broken for the planned analyses of data until all decisions on the evaluability of the data from each individual subject have been made and documented.

